2.0 Inclusion/Exclusion Criteria

Inclusion criteria:

- Pt undergoing VATS procedure at Indiana University Hospital
- ASA 1,2,3 or 4
- Age 18 or older, male or female
- Desires Regional anesthesia for postoperative pain control

Exclusion criteria:

- Any contraindication for Thoracic Epidural or Paravertebral block
- History of substance abuse in the past 6 months
- Patient staying intubated after surgery
- Known allergy or other contraindications to the study medications , which include dilaudid, bupivacaine, ropivacaine

3.0 Enrollment/Randomization

All VATS cases scheduled by thoracic surgeons at IU Health University Hospital will be identified. The subjects will be contacted face-to-face prior to surgery. They will be informed about the study and all questions will be answered. The potential subjects will be given a copy of the informed consent form and authorization form. The subjects will then be contacted face-to-face in POCU on the day of surgery and if participation is agreed, written consent will be taken.

A total of 120 subjects will be randomized by a computer program into three groups (40 per group):

1. US- Guided Paravertebral Catheter (PVB-A)- The Alaris pump will deliver 0.2% Ropivacaine at a rate of 10 ml/hr
2. Single Shot Paravertebral Block- placed by ultrasound using 0.2% Ropivacaine bolus.
3. Thoracic Epidural- The Alaris pump will deliver an epidural mixture of 0.125% bupiv/hydromorphone

Randomization will be stratified by prior opioid experience (opioid naïve or opioid tolerant). Separate randomization lists will be used for the two strata.

4.0 Study Procedures

All the thoracic epidurals and ultrasound-guided paravertebral blocks will be placed preoperatively. All procedures will be done using sterile technique with masks, hats, and sterile gloves. All procedures will be placed under the supervision of the attending anesthesiologist on the acute pain service or the attending anesthesiologist in the VATS room.

Thoracic epidurals will be placed using the Arrow thoracic epidural kit. Fentanyl and midazolam will be given prior to epidural placement. The epidural will be placed at the appropriate level to cover the entry site for the VATS procedure. Placement will be determined by anatomical landmarks. The epidural needle will be advanced toward the epidural space utilizing a Paramedian approach and loss-of-resistance technique. A sterile catheter will then be secured in place and the epidural infusion will be started at the end of the case.

Ultrasound guided paravertebral catheter and single shot paravertebral block will be accomplished using an ultrasound transducer at the thoracic level. This will be done using an in-plane or out-of-plane approach, at the discretion of the anesthesia staff performing the procedure. Then a needle will be inserted the needle into the paravertebral space and local anesthetic injected. Then a catheter will be placed within the injectate and secured in place in the case of the paravertebral catheter. The 0.2% Ropivacaine will be delivered by OnQ pump.

General anesthesia will be induced and the patient will be placed in the lateral position for the VATS procedure. The patients will be intubated with dual lumen endotracheal tubes and placed on one-lung ventilation for the procedure.

All patients will receive intravenous patient-controlled analgesia (PCA hydromorphone) post-operatively for breakthrough pain. Usual standard of care for pain control following a VATS procedure include scheduling PO acetaminophen and PO oxycodone PRN on POD 1 once patients tolerate diet.

Opioid usage at 1,24,48,72 hours after the block will be recorded by a member of the research team. Pain scores at rest and on movement (knee flexion) will be measured by the investigator using Visual Analog Scale (VAS). Nausea will be measured using a categorical scoring system (none=0; mild=1; moderate=2; severe=3). Sedation scores will also be assessed by a member of the study team using a sedation scale (awake and alert=0; quietly awake=1; asleep but easily roused=2; deep sleep=3). All these parameters will be measured at 1, 24, 48 and 72 hours after the epidural or PVB. Patients will be encouraged to ambulate on postoperative day 1 under supervision.

All catheters will be removed by APS (Acute Pain Service) while patients are still in the hospital. APS will continue to follow the patients until catheter removal. Patient's hospital length of stay and readmission rate will be recorded from NSQIP (National Surgical Quality Improvement Program) data.

All patients will receive a phone call 6 months after surgery for assessment for chronic post-surgical pain. Patients will be assessed by a member of the research team over the phone. They will be assessed on their pain score and narcotic usage by using the Brief Pain Inventory. Study participation will conclude after the 6 month follow questionnaire has been completed.

5.0 Reporting of Adverse Events or Unanticipated Problems involving Risk to Participants or Others

Patients will be monitored by the primary team during the postoperative period which is after surgery, through hours, 24, 48, and 72. We will also follow up in 6 months with a telephone call to complete a questionnaire which will conclude all study participation. The potential complications or risks associated with all three procedures are risks that are normally expected and we will not consider these adverse events. Any post-operative complication that is associated with the required medication per study protocol such as drug toxicity or nausea and vomiting related to taking the scheduled Tylenol and PRN (as needed) oxycodone for pain will be reported as an adverse event. This required drug regimen is specific to the study. All of these events will be reported to the Principal investigator and will be addressed immediately. These adverse events will be assessed to determine if they meet prompt reporting criteria, and if so, we will report these events to the IRB committee using the prompt reporting form. Events not promptly reportable will be reported to the IRB at the time of study renewal, if applicable."

Normal post-operative adverse events such as nausea, vomiting, and pruritus will not be considered a recordable or reportable event to the IRB since it's part of the post-operative course expected with these procedures.

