Previous studies have demonstrated that both thoracic epidurals and paravertebral blocks provide adequate analgesia for VATS. Thoracic epidurals provide excellent pain relief but are associated with hypotension and more nausea/vomiting. Paravertebral catheters have the advantage of having a lower side effect profile than thoracic epidurals. Paravertebral blocks have also been shown to improve respiratory function after surgery. Single shot paravertebral blocks have been described as providing adequate post-VATS pain control, despite a shorter duration of action compared to catheter. In order to evaluate the effectiveness and the side effects of the different pain modalities for post-VATS pain control, we will compare these three different methods of pain blocks:

- 1)single shot paravertebral block
- 2)paravertebral catheters
- 3)thoracic epidural

Rationale and Specific Aims

All of the pain control modalities allow for titration and continuous infusion of local anesthetic to achieve adequate pain control for the duration that the catheter remains in place, except for the single shot paravertebral block. The specific aim of the study is to compare the difference between the three pain blocks in achieving the following:

1. Improved postoperative pain scores
2. Decreased opioid requirements
3. Improved patient satisfaction scores
4. Decreased opioid side effects (Nausea, sedation, ileus, urinary retention, respiratory depression)

The primary endpoint of this study will be VAS pain score. The VAS scores will be taken with both rest and movement.

The secondary endpoint includes intravenous opioid consumption and opioid side effects (nausea, sedation, ileus, urinary retention, respiratory depression). The IV and PO opioid doses will be quantified at 1, 24, 48, and 72 hours. We will also measure postoperative nausea and sedation scores at 1, 24, 48, and 72 hours. We will also measure time to first bowel movement, incidence of urinary retention, incidence of respiratory depression, and time to discharge. If subjects are discharged prior to completing the 72-hour endpoints, efforts will be made to contact them and obtain data points. If unable to be reached, or unable to collect data, we will not consider these deviations since it will not change the integrity of the study data.

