7.0 Statistical Considerations

Primary outcome: VAS score at 24 and 48 hours

Primary Research Hypothesis: Thoracic epidural and Ultrasound guided paravertebral block with continuous catheter will provide lower pain scores compared to single shot paravertebral block.

Secondary outcomes: Opioid usage after 1, 24, 48 and 72 hours. Pain scores using VAS at rest and on movement at 1, 24, 48 and 72 hours. Patient satisfaction scores at 24 and 48 hours. Nausea scores at 1, 24, 48 and 72 hours. Sedation scores at 1, 24, 48 and 72 hours. Time to first bowel movement, incidence of urinary retention, and incidence of respiratory depression will be recorded as well.

Secondary Research Hypotheses: Thoracic epidural anesthesia and Ultrasound guided paravertebral catheter will show improved pain control, improved patient satisfaction scores, and decreased nausea and sedation scores compared to single shot paravertebral.

Statistical analysis will be performed using a standard statistical program (SAS or SPSS). All data will be summarized (means, standard deviations, standard errors, and ranges for continuous variables; frequencies and percentages for categorical variables) by group. Demographic data will be compared between the four groups using ANOVA or chi-square tests as appropriate. The primary outcome, VAS at 24 and 48 hours, will be compared between the groups using repeated measures ANOVA; the model will include fixed effects for group, time, and the group by time interaction and random effects to allow correlations between the two times and different variances for the two times. Pain and satisfaction scores and opioid usage over time will be analyzed using repeated measures ANOVA. Nausea and sedation scores will be compared between groups at each time point using Mantel-Haenszel chi-square tests for ordered categorical data. Distributions of the continuous variables will be examined, and a transformation of the data (e.g. natural logarithm) or nonparametric tests will be used as necessary. A 5% significance level will be used for all comparisons.

Based on prior studies, the coefficient of variation for the VAS score at 24 and 48 hours is estimated to be 0.70. With a sample size of 40 per group the study will be able to detect a 60% decrease in VAS score between any two groups, assuming two-sided tests each conducted at a 5% significance level.

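### The VAS on movement is provoked by knee flexion, which is not matched to thoracic surgery or thoracic blocks and is likely to be an insensitive measure of dynamic post-VATS pain

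*Combined protocol and SAP*

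**What the plan says.** Section 4.0 (Study Procedures) contains the only definition of movement in the protocol: "Pain scores at rest and on movement (knee flexion) will be measured by the investigator using Visual Analog Scale (VAS". These scores are taken at 1, 24, 48 and 72 hours after the block.

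The same section puts the interventions at the chest. For the epidural: "The epidural will be placed at the appropriate level to cover the entry site for the VATS procedure". The paravertebral catheter and the single-shot block "will be accomplished using an ultrasound transducer at the thoracic level".

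The status of the movement score differs between sections:

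- Section 1.0 (Rationale and Specific Aims): "The primary endpoint of this study will be VAS pain score", followed directly by "The VAS scores will be taken with both rest and movement".
- Section 7.0 (Statistical Considerations): "Primary outcome: VAS score at 24 and 48 hours", with no mention of rest or movement. The entry "Pain scores using VAS at rest and on movement at 1, 24, 48 and 72 hours" stands under the secondary outcomes.

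Section 4.0 also encourages supervised walking on the first postoperative day, but attaches no pain score to it.

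**The concern.** A movement score adds to a resting score only if the movement stresses the operated site. Knee flexion does not directly load the chest wall, so followed as written the rule may give a score close to the resting one under a different label. It may also pick up knee or hip pain unrelated to the operation; Section 2.0 sets no upper age limit.

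The protocol itself links the blocks to breathing ("Paravertebral blocks have also been shown to improve respiratory function after surgery"), yet no pain score is taken during a breath or a cough.

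At stake is the interpretation of a null result. The hypothesis in Section 7.0 is that the two continuous techniques give lower pain scores than the single shot, which Section 1.0 describes as shorter acting. If the provocation is insensitive, the arms could look alike on the movement VAS while differing in pain on coughing or deep breathing. Analysis cannot repair this, because no other dynamic score is collected.

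**Working it through.** **Step 1. Match between manoeuvre and site.**

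| Element | Location in the body | Source |
|---|---|---|
| Surgery | Chest (VATS) | Sections 1.0, 2.0 |
| Epidural | Level covering the VATS entry site | Section 4.0 |
| Both paravertebral techniques | Thoracic | Section 4.0 |
| Movement for the dynamic VAS | Knee | Section 4.0 |

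No reason is given for choosing the knee. That knee flexion does not directly load the chest wall is general anatomy, not a statement in the documents. Some indirect trunk movement is possible.

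**Step 2. What enters the primary model.** The repeated measures model in Section 7.0 has group, time and their interaction, with correlation across the two times. It has no rest/movement factor, so as described it takes one VAS value per patient per time. Section 7.0 does not say whether that value is the rest score, the movement score or a combination. Movement VAS may be all, part or none of the primary outcome.

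**Step 3. The plan's own figure.** Inputs from Section 7.0: coefficient of variation 0.70, 40 per group, two-sided 5% per test, 60% decrease. No power is stated, so 40 per group has no single target to reproduce. By the normal approximation for two means at one time point,

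power = Φ(Δ / (σ√(2/n)) − 1.96).

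- Raw scale (reference mean 1): σ = 0.70, Δ = 0.60. Then 0.70 × √(2/40) = 0.1565, 0.60 / 0.1565 = 3.83, and Φ(1.87) = 0.97.
- Log scale: σ = √ln(1 + 0.70²) = 0.631, Δ = −ln(0.4) = 0.916, giving power above 0.999.

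The stated 60% decrease is therefore detectable. At 80% power, 40 per group detects a decrease of 44% on the raw scale or 33% on the log scale.

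**Step 4. Sensitivity to dilution (assumption, not in the documents).** Suppose the true dynamic difference is 60%, knee flexion captures a fraction f of it, and the SD is unchanged. Then Δ = 0.60f on the raw scale and −ln(1 − 0.60f) on the log scale.

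| f | Power, raw | Power, log |
|---|---|---|
| 1 | 0.97 | >0.999 |
| 0.75 | 0.82 | 0.99 |
| 0.5 | 0.48 | 0.71 |
| 0.25 | 0.16 | 0.21 |

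Power falls below 80% once f is under about 0.73 on the raw scale (0.4385 / 0.60) or 0.54 on the log scale (0.3267 / 0.60). A two-sample t-test changes the raw-scale values by about 0.01. Extra variance from leg pain would lower all of them further.

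**The case against.** Four points can be made against the concern.

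- **Primary status.** A reader of Section 1.0 might infer that half of the primary endpoint is invalid. Section 7.0 does not support that: it lists rest and movement VAS as secondary and leaves the primary VAS unspecified. This objection stands.
- **Strength of the claim.** A reader might also infer that the trial cannot measure dynamic pain, or that knee flexion captures none of it. Nothing in the documents establishes zero capture. What can be defended is a poor match and probable insensitivity. This stands too.
- **No separate objective on dynamic pain.** The aims and hypotheses speak of pain scores in general, and rest VAS, opioid use, satisfaction and side effects are untouched. The hypothesis can still be tested at rest. This limits the damage, but the plan does collect and analyse movement VAS at four times, and that result needs a meaning.
- **Same manoeuvre in every arm.** Under randomisation, leg pain adds noise and does not favour an arm. That is correct. It answers a charge of bias towards one technique, but not dilution of a real difference.

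None of these points gives a reason for choosing knee flexion.

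**Conclusion.** The concern holds in a limited form and should be fixed. The only manoeuvre defined for the movement VAS is a leg movement, in a trial of chest surgery and thoracic blocks, so this score at all four times is likely to be insensitive to dynamic post-VATS pain and to dilute group differences.

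The size is unknown. The range in the working, from almost no loss of power to most of it, depends entirely on the assumed capture fraction and on the analysis scale, and the documents do not locate knee flexion within it. The underlying judgement rests on general anatomy.

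Rest VAS is unaffected. Whether the primary outcome is affected depends on which section is followed: it is if movement VAS enters the primary model, as Section 1.0 allows, and it is not if the primary VAS is the rest score. The point gives no reason to change the sample size; more patients would not correct a score that is poorly matched to the pain under study.

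**What to change.** 1. In Section 4.0, replace knee flexion with one standardised chest-wall manoeuvre, for example a voluntary cough or a deep inspiration, performed identically in all arms and at 1, 24, 48 and 72 hours.
2. Use the same definition wherever Sections 1.0 and 7.0 refer to movement.
3. Reconcile Sections 1.0 and 7.0 by stating whether rest VAS or movement VAS is the primary outcome at 24 and 48 hours. Make this choice before any comparison between arms is seen.

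The cost is a short amendment and a change to the case report form; visits, assessor and scale stay the same. The downside is that scores already taken with knee flexion should not be pooled with the new ones and would be reported separately. The documents do not say how many such scores exist. If movement VAS is named as primary, losing them from the pooled analysis would be a material cost, which favours amending early.

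### The 1-hour readings are timed from a block placed before surgery, so they are not postoperative whenever surgery ends 1 hour or more after the block

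*Combined protocol and SAP*

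**What the plan says.** Section 4.0 (Study Procedures) sets the clock for the repeated measurements. For opioid use: "Opioid usage at 1,24,48,72 hours after the block will be recorded". For VAS at rest and on movement, nausea and sedation: "All these parameters will be measured at 1, 24, 48 and 72 hours after the epidural or PVB".

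The same section says when the block is done: "All the thoracic epidurals and ultrasound-guided paravertebral blocks will be placed preoperatively". Surgery follows: "General anesthesia will be induced and the patient will be placed in the lateral position for the VATS procedure", and "The patients will be intubated with dual lumen endotracheal tubes and placed on one-lung ventilation for the procedure". Two analgesic components begin only afterwards. In the epidural arm "the epidural infusion will be started at the end of the case", and for everyone "All patients will receive intravenous patient-controlled analgesia (PCA hydromorphone) post-operatively for breakthrough pain".

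The rationale and aims under section 1.0 describe some of these readings differently: "We will also measure postoperative nausea and sedation scores at 1, 24, 48, and 72 hours". They also name better postoperative pain scores as an aim, without attaching hours to it. Section 5.0 describes the postoperative period as the time after surgery.

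Section 7.0 lists VAS, opioid use, nausea and sedation at all four times as secondary outcomes and names no time origin. The primary outcome is VAS at 24 and 48 hours.

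**The concern.** The protocol uses two clocks, one from the block and one from surgery, and never reconciles them. For the 24, 48 and 72 hour readings the difference is a modest shift. For the 1-hour reading it can decide whether the patient is in recovery or on the operating table.

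If surgery is still under way at hour 1, the patient is anesthetized and intubated. VAS at rest and on knee flexion cannot be obtained, nausea cannot be reported, and a sedation score describes the anesthetic. The postoperative PCA has not started, and neither has the epidural infusion, so opioid use to that point says nothing about postoperative need.

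These values enter the analysis. Section 7.0 tests nausea and sedation between groups at each time point, so hour 1 has its own tests. It analyzes pain and opioid use over time by repeated measures ANOVA. At stake is whether the 1-hour secondary outcomes can be read as postoperative outcomes at all.

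**Working it through.** The plan gives no figure to reproduce here. The check is timing arithmetic plus a count of values.

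**Inputs**
- Reading times t = 1, 24, 48 and 72 hours, counted from the block (section 4.0).
- Block before surgery in all three arms (section 4.0).
- 120 subjects (section 3.0).
- Five measures taken at all four times: rest VAS, movement VAS, nausea, sedation and opioid use (sections 4.0 and 7.0).
- T, the hours from block to end of surgery. The documents give no value, so T is an assumption and is varied.

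**Timing.** Time of a reading relative to end of surgery = t − T. Results in hours:

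| T (assumed) | t = 1 | t = 24 | t = 48 | t = 72 |
|---|---|---|---|---|
| 0.5 | +0.5 | 23.5 | 47.5 | 71.5 |
| 1 | 0 | 23 | 47 | 71 |
| 2 | −1 | 22 | 46 | 70 |
| 3 | −2 | 21 | 45 | 69 |

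The 1-hour reading is postoperative only if 1 − T > 0, that is, T < 1 hour. That hour would have to hold induction, intubation, positioning and the whole procedure. The later readings remain postoperative throughout this range.

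**Values exposed**
- Scheduled values: 5 × 4 × 120 = 2,400.
- At hour 1: 5 × 120 = 600, and 600 / 2,400 = 25%.
- Nausea and sedation at hour 1: 2 × 120 = 240.
- For each 10% of subjects with T of 1 hour or more: 0.10 × 120 = 12 subjects, 12 × 5 = 60 values, of which 12 × 2 = 24 are nausea or sedation.
- Range: 0 if T is below 1 hour in all subjects; 600 if it is 1 hour or more in all.

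**How firm the conflict is, by measure**
- Nausea and sedation: explicit. Section 1.0 labels them postoperative at the same hours, including hour 1, while section 4.0 counts those hours from the preoperative block.
- VAS: less direct. Section 1.0 states a postoperative aim but gives no hours with it.
- Opioid use: an inference from the order of events and the postoperative start of PCA.

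**The case against.** The strongest reply is that this is loose wording. Sections 1.0 and 5.0 suggest that postoperative readings were intended, and staff would presumably take the first reading in recovery rather than seek a VAS from an anesthetized patient. That may well be the intent. But staff who did so would be departing from section 4.0 and using an origin the protocol does not define, and different assessors could choose different ones. Reading the epidural clock as starting with the infusion does not help: the text does not say so, it cannot cover the single-shot arm, and it would give the arms different origins.

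A second point is that T is assumed and the count depends on it. This stands. The documents support no single count, only the range from 0 to 600. The 25% is simply one time point in four, and adding satisfaction at 24 and 48 hours (2 × 120 = 240 values) would make it 600 / 2,640 = 22.7%. Opioid doses given by hour 1 can also still be recorded, although they would not measure postoperative use.

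A third is that a block clock is legitimate when techniques of different duration are compared. This is right for the later readings, since section 1.0 itself notes that a single-shot block lasts less long than a catheter. It does not rescue an intraoperative reading that is meant to be postoperative.

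Finally, only secondary outcomes are exposed. That is correct, and it limits the weight of the point.

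**Conclusion.** The concern holds and should be fixed. As written, section 4.0 yields 1-hour VAS, nausea, sedation and opioid values that cannot serve as postoperative outcomes in any subject whose surgery ends 1 hour or more after the block. The number affected rests on T, which must be assumed. The mismatch between sections 1.0 and 4.0 over the origin for nausea and sedation does not depend on T.

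The primary outcome is not undermined: at T of 1 to 3 hours its two readings fall 23 to 21 and 47 to 45 hours after surgery. No bias between arms, loss of power or change in sample size is claimed.

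**What to change.** - In section 4.0, tie the 1-hour reading in all three arms to one postoperative time zero, for example the end of surgery.
- State the time zero for the 24, 48 and 72 hour readings. Keeping them on the block clock is defensible; moving them to the postoperative clock is also possible.
- Make sections 1.0 and 7.0 name the same origin or origins.
- Record block time and end-of-surgery time for each subject, so that time since block can still be examined.

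The cost is a few wording changes and at most two time fields on the case report form, with no extra assessments. The form is not among the documents, so these times may already be collected.

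There is one trade-off. If only the first reading moves to 1 hour after the end of surgery, the gap to the 24-hour reading becomes 24 − (T + 1) = 23 − T hours: 22, 21 and 20 hours for T = 1, 2 and 3, instead of 23. This varying interval does no harm if time is a categorical factor in the repeated measures ANOVA, and section 7.0 should say that it is. If all readings move, the gap stays at 23 hours but the later readings leave the block clock.

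### No pain measure is taken before the block, so 6-month pain cannot be read as post-surgical and the primary VAS model has no baseline to use

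*Combined protocol and SAP*

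**What the plan says.** **Timing of pain scores.** Section 4.0 (Study Procedures) fixes the schedule for pain, nausea, sedation and opioid use: "All these parameters will be measured at 1, 24, 48 and 72 hours after the epidural or PVB". Section 7.0 (Statistical Considerations) repeats it: "Pain scores using VAS at rest and on movement at 1, 24, 48 and 72 hours". The clock starts before the operation, because "All the thoracic epidurals and ultrasound-guided paravertebral blocks will be placed preoperatively".

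**Six months.** Section 4.0 continues: "All patients will receive a phone call 6 months after surgery for assessment for chronic post-surgical pain". The instrument is named next: "They will be assessed on their pain score and narcotic usage by using the Brief Pain Inventory". Section 1.0 gives pain 6 months after surgery as a study aim. Section 7.0 does not list a 6-month outcome and gives no analysis for one.

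**Before surgery.** Section 3.0 plans a contact at which consent is taken: "The subjects will then be contacted face-to-face in POCU on the day of surgery". It also states: "Randomization will be stratified by prior opioid experience", with separate lists for opioid-naïve and opioid-tolerant patients. Section 2.0 excludes recent substance abuse but not chronic pain.

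**Primary model.** For VAS at 24 and 48 hours, section 7.0 says "the model will include fixed effects for group, time, and the group by time interaction", plus random effects for the correlation and unequal variances of the two times. Neither a baseline score nor the opioid stratum is among the terms.

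**The concern.** The trial expects some patients who used opioids before surgery, since it makes them a stratum, and nothing excludes patients with existing pain. If such a patient reports pain or narcotic use at 6 months, the data cannot show whether it began with the operation, got worse, or was there all along. The label in section 4.0 attributes it to surgery, and the planned data cannot support that attribution.

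The 1-hour score does not fill the gap. It follows the block and, with blocks placed pre-operatively, may fall during surgery.

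For the primary outcome, pain before the block may predict pain at 24 and 48 hours. If it does, leaving it out gives up precision that cannot be recovered once a patient has had surgery.

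**Working it through.** **Inputs from the documents (sections 3.0 and 7.0):** 40 per group; coefficient of variation 0.70; two-sided 5% level for each comparison; stated detectable decrease 60%. **Assumed, because the documents give no value:** the correlation r between baseline and later VAS, and all 6-month pain rates.

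**1. The plan's own figure.** The 60% cannot be strictly reproduced because no power is stated. Take the control mean as 1, the SD as 0.70 on the raw scale, and one two-group comparison at one time point (normal approximation):

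- Standard error = 0.70 × √(2/40) = 0.1565.
- Power for a 60% decrease: 0.60/0.1565 − 1.96 = 1.87, which gives 97.0%.
- Decrease detectable with 80% power: (1.96 + 0.842) × 0.1565 = 0.44, or 44%.

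**2. Adding a baseline VAS.** The residual variance is multiplied by 1 − r², and the detectable decrease by √(1 − r²).

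| r (assumed) | 1 − r² | Fall in variance | Decrease detectable, 80% power | Power for 60% decrease |
|---|---|---|---|---|
| 0 | 1.00 | 0% | 44% | 97.0% |
| 0.3 | 0.91 | 9% | 42% | 98.0% |
| 0.5 | 0.75 | 25% | 38% | 99.3% |

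The gain matters little for the plan's own 60% target and more for smaller differences.

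**3. Make-up of 6-month cases, if any pain counts as a case.** Assume 15% pre-existing and 20% new pain.

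- If the two groups do not overlap: 0.15/(0.15 + 0.20) = 0.43.
- If new pain arises in 20% of those without prior pain: 0.15/(0.15 + 0.20 × 0.85) = 0.15/0.32 = 0.47.

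**4. Range, and the effect on a yes/no comparison.** Assume new pain of 30% in one arm and 15% in another, and pre-existing pain q in both. The observed rate is q + (1 − q) × new rate, so the difference is (1 − q) × 15 points. Power is for 40 per arm, two-sided 5%.

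| q (assumed) | Observed rates | Difference | Power | Pre-existing share of cases, by arm |
|---|---|---|---|---|
| 0% | 30.0% vs 15.0% | 15.0 points | 36% | 0% and 0% |
| 10% | 37.0% vs 23.5% | 13.5 points | 26% | 27% and 43% |
| 20% | 44.0% vs 32.0% | 12.0 points | 20% | 45% and 62.5% |
| 30% | 51.0% vs 40.5% | 10.5 points | 15% | 59% and 74% |

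**5. The same question for a score.** If 6-month pain is compared as a mean score, and prior pain is independent of arm and simply adds to new pain, it cancels from the expected difference and only adds variance. The shrinkage in step 4 therefore belongs to the yes/no analysis alone.

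**The case against.** The strongest reply is that randomization makes prior pain alike across arms on average. A comparison of 6-month pain then answers the aim in section 1.0 without a baseline. That stands. A reader might infer that the arm comparisons are biased or that the primary test is invalid; the documents support neither.

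A reader might also infer that any 6-month arm difference must be diluted. The plan defines no 6-month case, threshold or incidence endpoint. Dilution follows only if the outcome is reduced to any pain, yes or no, and the plan does not say that it will be.

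Opioid status is known before randomization, so opioid-tolerant patients can be identified at analysis. That helps in part. But it is a two-level opioid history, not a pain score, and the model as written does not use it.

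The gain for the primary VAS may be small, or nil if r is near 0. That also stands, and it makes the 6-month part the weightier one.

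Finally, the 6-month outcome is absent from section 7.0, and section 1.0 does not count a missed questionnaire as a deviation. This lowers its rank among the outcomes. It does not remove the aim stated in section 1.0 or the label in section 4.0.

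**Conclusion.** The point holds as a limit on interpretation and precision, not on validity. As planned, the trial can report pain at 6 months by arm but cannot say how much of it is post-surgical. With 15% pre-existing and 20% new pain, 43% to 47% of any-pain cases would be pre-existing. Those rates are assumed, and the share moves widely with them, as the range above shows.

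For the primary VAS the loss is modest. The detectable decrease at 80% power would move from 44% to 42% (r = 0.3) or 38% (r = 0.5), and not at all at r = 0. These figures rest on assumed correlations, the raw scale, and a single time point rather than the full two-time model.

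The change is worth making because the remedy is cheap and a patient's baseline cannot be collected prospectively after surgery.

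**What to change.** - **Collect.** At the existing POCU contact, after consent and before any pre-block sedation, record VAS at rest and on movement and the Brief Pain Inventory with current narcotic use. The order matters because section 4.0 describes fentanyl and midazolam before epidural placement, so a score taken after sedation would not be a clean baseline.
- **Primary model (section 7.0).** Add the opioid stratum, which is already known and costs nothing, and baseline VAS.
- **Six months.** Add the outcome to section 7.0. Analyse Brief Pain Inventory scores adjusted for their baseline, and report new or worsened pain rather than any pain.
- **Patients already enrolled.** State that they lack a baseline and describe their results as pain at 6 months, without the post-surgical label.

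The cost is one form and a few minutes per patient on the day of surgery, at a contact already planned.
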